10.0 Conventions and Derivations

10.1.1 Method for Handling Missing Data

There will be no imputation of incomplete or missing data unless otherwise specified in this SAP.

Please refer to Appendix 3 for specific data handling rules, including missing last dose date for the interim analysis, missing severity/relationship of adverse events, incomplete/missing dates for adverse events and prior/concomitant medications, interpretation of non-numeric results (e.g. “< BLQ”, “>x.xx”) from PK and laboratory measures, etc.

10.1.2 Definition of Baseline and Change from Baseline Values

Unless otherwise specified, Baseline is defined as the last non-missing measurements prior to the first dose of study drug.

The ECG Baseline and post-Baseline values are averages of the triplicate assessments. The change from Baseline is the difference between the post-Baseline and Baseline averages.

In analyses of pharmacodynamics (PD), including specialty hematology parameters, Baseline is defined as the average of non-missing values from the screening and Baseline visits. PD assessments include laboratory measurements based on blood samples as listed in sections 13.6.7 and 13.6.8.

10.1.3 Definition of Study Days

Study Day 1 is defined as the date on which subjects are administered their first dose of study drug. For visits (or events) that occur on or after the date of the first dose of study drug, study day is defined as (date of visit [event] – date of first dose of study drug + 1). For visits (or events) that occur prior to Study Day 1, study day is defined as (date of visit [event] – date of first dose of study drug). There is no Study Day 0.

10.1.4 Definition of Treatment-Emergence

A treatment-emergent adverse event (TEAE) is defined as an AE that starts after initiation of study drug, or an AE that existed pre-treatment and worsened in severity after initiation of study drug, through 30 days after the last dose of study drug.

10.1.5 Red Blood Cell Transfusion Reduction: 12-Week Fixed Interval

Transfusion burden will be measured using a “fixed” 12-week time interval. The 12-week intervals used for analysis are defined as:

Pre-treatment 12-week interval: from Day -83 to Day 1;

Week 13–24 interval: from Day 86 to Day 169;

Week 25–36 interval: from Day 170 to Day 253.

10.1.6 Red Blood Cell Transfusion Reduction: 24-Week Fixed Interval

Transfusion burden will also be measured using a “fixed” 24-week time interval. The 24-week intervals used for analysis are defined as below.

Pre-treatment 12-week interval: from Day -83 to Day 1;

Week 13–36 interval: from Day 86 to Day 253.

10.1.7 Red Blood Cell Transfusion Reduction: 12-Week Rolling Interval

Transfusion reduction will also be measured using any consecutive “rolling” 12-week time intervals during the study, e.g., Days 2 to 85, Day 3 to 86 and so on, compared to the pre-treatment 12-week interval (from Day-83 to Day 1). A transfusion occurring on Day 1 belongs to the pre-treatment period.

10.1.8 Red Blood Cell Transfusion Reduction: 14-Week Rolling Interval

Transfusion reduction will also be measured using any consecutive “rolling” 14-week time intervals during the study, e.g., Days 2 to 99, Day 3 to 100 and so on. Day 1 transfusion belongs to baseline.

10.1.9 Quality of Life Assessments

Quality of life will be assessed using the TranQOL and SF-36 QoL tools in the TDT population and the NTDT-PRO and SF-36 QoL tools in the NTDT population.

The TranQOL (Klaassen 2013; Klaassen 2014. See protocol section 16.) is a disease-specific QoL measure for children and adults with thalassemia major. It has four versions: (i) a child self-report; (ii) an adult self-report; (iii) a parent self-report (measuring the impact of the disease on the parent), and (iv) a parent proxy report (measuring the child’s QoL). The questionnaire length ranges from 29 items (child) to 39 items (parent). The questions are grouped into 4 domains: physical health, emotional health, family functioning, and school and career functioning. The adult and parent self-report questionnaires include a fifth category on sexual activity which is only one item. For this study, only the adult self-report will be used which includes 36 items and an open-ended question: “Was there anything else that bothered you?”. The mean TranQOL score for each domain ranges from 0 to 100 with higher scores indicating higher QoL. Derivations for domain scores are specified in Section 13.6.6.1. A within-patient clinically meaningful change from baseline was defined as a ≥ 4 -point change for the TranQOL total score (Cappellini 2020). The criteria may be modified based on further research.

The SF-36 (Hays 2004. See protocol section 16.) is a 36-item, patient reported survey of patient health. The SF-36 consists of 8 scaled scores, which are the weighted sums of the questions in their section. Each scale is directly transformed into a 0 to 100 scale based on each scale having equal weight. The lower the score the more disability and the higher the score the less disability (i.e., a score of 0 is equivalent to a maximum disability and a score of 100 is equivalent to no disability). The 8 sections are: vitality, physical functioning, bodily pain, general health perceptions, physical role functioning, emotional role functioning, social role functioning, and mental health. Derivations for the scales and component scores are specified in Section 13.6.6.1. A within-patient clinically meaningful change from baseline was defined as 3.8–7.0-point improvement, based on the prespecified domain-specific cutoff values for the domains of the SF-36 questionnaire (Cappellini 2020).

The NTDT-PRO (Taher 2019. See protocol section 16.) is a new disease-specific health-related QoL tool for patients with NTDT. The NTDT-PRO was designed as a daily diary with recall of thalassemia-related symptoms over the previous 24 hours. The relatively short recall period is used due to the high level of day-to-day variation in symptoms experienced by patients with NTDT. The 6 NTDT-PRO items assess the presence or severity of specific symptoms using a numerical rating scale ranging from 0 (“absent/minimal”) to 10 (“extreme/high”): tiredness with or without physical activity, weakness with or without physical activity, and shortness of breath (SOB) with or without physical activity. NTDT-PRO items are grouped into 2 domains: tiredness/weakness (T/W) (tiredness with physical activity, tiredness without physical activity, weakness with physical activity, and weakness without physical activity) and shortness of breath (shortness of breath with physical activity, shortness of breath without physical activity). The total score is an average of the responses to questions 1–6. For this study, the NTDT-PRO will not be used as a daily diary; data will be collected at Baseline and at Weeks 12, 24, and 36. Derivations for domain scores and the total score are specified in Section 13.6.6.3.

10.1.10 Windowing Conventions

All scheduled study visits are defined relative to Study Day 1, the date of first dose. Scheduled visit windows are defined in Appendix 3. A windowing convention will be used to determine the analysis visit value for a given measurement and will be applicable for all by-visit summaries and analyses for efficacy and safety data. Refer to Table 1 (TDT) and Table 2 (NTDT) for specific visit windows.

Table 1: Visit Windows for Efficacy and Safety Analyses – TDT Population

Safety Analyses – Vital Signs and Weight	
Scheduled Study Visit (Protocol Scheduled Day)	Analysis Visit Window (Study Day)
Baseline	≤ 1
Week 1 (Day 7 ± 2)	2 to 15
Week 3 (Day 21 ± 7)	16 to 32
Week 6 (Day 42 ± 7)	33 to 53
Week 9 (Day 63 ± 7)	54 to 74
Week 12 (Day 84 ± 7)	75 to 95
Week 15 (Day 105 ± 7)	96 to 116
Week 18 (Day 126 ± 7)	117 to 137
Week 21 (Day 147 ± 7)	138 to 158
Week 24 (Day 168 ± 7)	159 to 179
Week 27 (Day 189 ± 7)	180 to 200
Week 30 (Day 210 ± 7)	201 to 221
Week 33 (Day 231 ± 7)	222 to 242
Week 36 (Day 252 ± 7)	243 to 267
Week 40 (Day 280 ± 7)	≥ 268
Safety Analyses – 12-Lead ECG, Hematology (Except Specialty Hematology) and Chemistry	
Scheduled Study Visit (Protocol Scheduled Day)	Analysis Visit Window (Study Day)
Baseline	≤ 1
Week 1 (Day 7 ± 2)	2 to 15
Week 3 (Day 21 ± 7)	16 to 32
Week 6 (Day 42 ± 7)	33 to 64
Week 12 (Day 84 ± 7)	65 to 106
Week 18 (Day 126 ± 7)	107 to 148
Week 24 (Day 168 ± 7)	149 to 190
Week 30 (Day 210 ± 7)	191 to 232
Week 36 (Day 252 ± 7)	233 to 267
Week 40 (Day 280 ± 7)	≥ 268
Safety Analyses – Urinalysis	
Scheduled Study Visit (Protocol Scheduled Day)	Analysis Visit Window (Study Day)
Baseline	≤ 1

Week 3 (Day 21 ± 7)	2 to 53
Week 12 (Day 84 ± 7)	54 to 127
Week 24 (Day 168 ± 7)	128 to 211
Week 36 (Day 252 ± 7)	≥212
Safety Analyses – Coagulation	
Scheduled Study Visit (Protocol Scheduled Day)	Analysis Visit Window (Study Day)
Baseline	≤ 1
Week 12 (Day 84 ± 7)	2 to 127
Week 24 (Day 168 ± 7)	128 to 211
Week 36 (Day 252 ± 7)	≥212
Efficacy Analyses – Specialty Hematology	
Scheduled Study Visit (Protocol Scheduled Day)	Analysis Visit Window (Study Day)
Baseline	≤ 1
Week 3 (Day 21 ± 7)	2 to 53
Week 12 (Day 84 ± 7)	54 to 106
Week 18 (Day 126 ± 7)	107 to 148
Week 24 (Day 168 ± 7)	149 to 190
Week 30 (Day 210 ± 7)	191 to 232
Week 36 (Day 252 ± 7)	≥233
Efficacy Analyses- PD Biomarkers	
Scheduled Study Visit (Protocol Scheduled Day)	Analysis Visit Window (Study Day)
Baseline	≤ 1
Week 3 (Day 21 ± 7)	2 to 53
Week 12 (Day 84 ± 7)	54 to 106
Week 18 (Day 126 ± 7)	107 to 148
Week 24 (Day 168 ± 7)	149 to 211
Week 36 (Day 252 ± 7)	≥212
QoL	
Scheduled Study Visit (Protocol Scheduled Day)	Analysis Visit Window (Study Day)
Baseline	≤ 1
Week 12 (Day 84 ± 5)	2 to 127
Week 24 (Day 168 ± 7)	128 to 211
Week 36 (Day 252 ± 7)	≥212

Table 2: Visit Windows for Efficacy and Safety Analyses – NTDT Population

Safety Analyses – Vital Signs, Weight, 12-Lead ECG, Hematology (Except Specialty Hematology) and Chemistry	
Scheduled Study Visit (Protocol Scheduled Day)	Analysis Visit Window (Study Day)
Baseline	≤ 1
Week 1 (Day 7 ± 2)	2 to 18
Week 4 (Day 28 ± 5)	19 to 43
Week 8 (Day 56 ± 7)	44 to 71
Week 12 (Day 84 ± 7)	72 to 99
Week 16 (Day 112 ± 7)	100 to 127
Week 20 (Day 140 ± 7)	128 to 155
Week 24 (Day 168 ± 7)	156 to 183
Week 28 (Day 196 ± 7)	184 to 211
Week 32 (Day 224 ± 7)	212 to 239
Week 36 (Day 252 ± 7)	240 to 267
Week 40 (Day 280 ± 7)	≥ 268
Safety Analyses – Urinalysis	
Scheduled Study Visit (Protocol Scheduled Day)	Analysis Visit Window (Study Day)
Baseline	≤ 1
Week 4 (Day 28 ± 5)	2 to 57
Week 12 (Day 84 ± 7)	58 to 127
Week 24 (Day 168 ± 7)	128 to 211
Week 36 (Day 252 ± 7)	≥212
Safety Analyses – Coagulation	
Scheduled Study Visit (Protocol Scheduled Day)	Analysis Visit Window (Study Day)
Baseline	≤ 1
Week 12 (Day 84 ± 7)	2 to 127
Week 24 (Day 168 ± 7)	128 to 211
Week 36 (Day 252 ± 7)	≥212
Efficacy Analyses – Specialty Hematology	
Scheduled Study Visit (Protocol Scheduled Day)	Analysis Visit Window (Study Day)
Baseline	≤ 1
Week 4 (Day 28 ± 5)	2 to 57

Week 12 (Day 84 ± 7)	58 to 127
Week 24 (Day 168 ± 7)	128 to 211
Week 36 (Day 252 ± 7)	≥212
Efficacy Analyses- PD Biomarkers	
Scheduled Study Visit (Protocol Scheduled Day)	Analysis Visit Window (Study Day)
Baseline	≤ 1
Week 4 (Day 28 ± 5)	2 to 57
Week 12 (Day 84 ± 7)	58 to 127
Week 24 (Day 168 ± 7)	128 to 211
Week 36 (Day 252 ± 7)	≥212
QoL	
Scheduled Study Visit (Protocol Scheduled Day)	Analysis Visit Window (Study Day)
Baseline	≤ 1
Week 12 (Day 84 ± 5)	2 to 127
Week 24 (Day 168 ± 7)	128 to 211
Week 36 (Day 252 ± 7)	≥212

Windowing will be applied prior to any missing data calculations. The last non-missing measurement taken prior to the date of first dose (including unscheduled assessments) will be labeled as “Baseline”. Screening visits that occurred before the Baseline visit will not be assigned an analysis visit. The early discontinuation visit will be eligible for allocation to an analysis visit.

If one or more results for a variable are assigned to the same analysis visit, the result with the date closest to the protocol scheduled day will be used in the analysis. If 2 measurements in the same analysis visit window are equidistant from the protocol scheduled study day, the earliest measurement will be used in the analysis. If multiple assessments are available on the same day (for the same time point), then the average of the assessment will be used in the analysis. If both central and local assessments of the same lab test are available for the same visit, the central result will take precedence over the local result if baseline is collected centrally. If a scheduled assessment is missing, due to clotting for example, and an unscheduled retest assessment is available in the visit window for the scheduled visit, the unscheduled retest assessment may be used in place of the missing scheduled assessment.

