**Duration of Treatment and Study Duration:**

The planned maximum duration of study participation is approximately 44 weeks. This consists of a screening period of up to 4 weeks, a treatment period of 36 weeks, and a 4-week safety follow-up assessment after the last dose of study drug is administered. In addition, there is retrospective data review undertaken at the start of subject participation that aims to collect information on transfusion activity during the 12 weeks preceding the Baseline (Day 1) visit (historical transfusion burden).

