11.4 Per Protocol Analysis Set

The Per Protocol Analysis Set will include all subjects in the Safety Analysis Set who have provided sufficient data without major protocol deviations or events that would be expected to affect the analysis. Sufficient data is defined as any post-baseline assessment and subject did not discontinue prior to week 12 for reasons other than AEs. The PP Analysis Set will be identified based on blinded data prior to unblinding the final analysis dataset, and the TDT and NTDT populations may have their PP Analysis Set components defined at different times. The PP Analysis Set will be the primary analysis set used for PD and efficacy analyses. Subjects will be analyzed according to their randomized treatment.

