The mean changes from Baseline to Week 36 for serum ferritin will be assessed using ANCOVA models with baseline value as a covariate on the Safety Analysis Set. The Baseline mean serum ferritin will be calculated during the 12 weeks prior to the first dose of study drug. The post-baseline (Week 36) mean values will be calculated during the last 12 weeks of the 36-week treatment period, or the last 12 weeks of study drug for subjects who are discontinued early. Summary statistics for observed values at Baseline and Week 36 and change from Baseline to Week 36 of serum ferritin will be presented. The change from baseline in mean serum ferritin at Week 36 will be analyzed using an ANCOVA model with baseline serum ferritin mean as a covariate. LSMean estimates and 95% CIs will be presented for each active arm and placebo at Week 36. The LSMean difference estimates and associated 95% CIs and p-values at Week 36 will also be reported for each active arm vs. placebo and the combined active arms vs. Placebo. Line plots will be provided for mean change from Baseline with 95% CI to Week 36 for serum ferritin by treatment arm. The values at Week 24 will be analyzed in a similar manner.

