13.6.4.3 NTDT Population

Responder Analyses

Proportion of Subjects with an Increase from Baseline of $\geq 3\%$ in Mean HbF Endpoint

The proportion of subjects with increase from Baseline of $\geq 3\%$ in mean HbF values (at Weeks 12 to 24 and Weeks 24 to 36) will be assessed using a CMH test. The number and percentage of responders and non-responders at Weeks 12-24 and Weeks 24-36 will be presented for each treatment arm as well as ORs, 95% CIs, and p-values from the CMH tests. The difference in proportions (active arm-Placebo and the combined active arms-Placebo) and corresponding 95% CI will be also provided. Bar plots will be provided. The proportion of subjects with response in HbF, where a responder has an increase of $\geq 3\%$ at Weeks 12-24 and Weeks 24-36 compared to Baseline, Odds ratios, 95% CI, and p values will be displayed by treatment arm.

Proportion of Subjects with an Increase from Baseline of $\geq 1.0 \text{ g/dL}$ in Mean Hb Endpoint

The proportion of subjects with increase from Baseline of $\geq 1.0 \text{ g/dL}$ in mean Hb values (at Weeks 12 to 24 and Weeks 24 to 36) will be evaluated using a Cochran-Mantel-Haenzel (CMH) test to compare the proportion of subjects who achieved improvement between the placebo group and each of the 2 active treatment arms (IMR-687 lower dose and IMR-687 higher dose) and the combined active arms. The number and percentage of responders and non-responders, ORs, 95% CIs, p-values from the CMH tests and the difference in proportions and corresponding 95% CI will be provided similarly to the HbF above.

Mean Change Analyses

Change from Baseline in Mean Hb and HbF Endpoints

The Baseline value of Hb will be defined as the mean of the screening and baseline Hb values. The Baseline value of HbF will be defined in an analogous manner. Post-Baseline Hb is defined as the mean of all documented hemoglobin values collected during each 12-week interval. If there are any missing values at scheduled collected times, the mean will still be calculated from the remaining non-missing values. However, any Hb values collected within 8 weeks after a transfusion will not be included in the calculation of the mean. Post-Baseline HbF will be defined in an analogous manner. To estimate the change of Hb and HbF after dosing within each 12-week interval (Week 12-24, week 24-36), summary statistics for the Baseline, post-Baseline, and change from Baseline Hb and HbF will be provided by treatment arm.

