13.6.6.3 NTDT Population

Proportion of Subjects who have an Hb Increase of ≥ 1.0 g/dL Endpoints

The number and percentage of subjects who have an Hb increase of ≥ 1.0 g/dL from Baseline for ≥ 14 days in the absence of RBC transfusions will be calculated at all post-Baseline Hb collection time points. All Hb values, including those collected at unscheduled visits but excluding values collected within 8 weeks after a RBC transfusion, will be sorted by date. For each value and the next subsequent value in time, the values and the time between values will be compared. If both values are increased ≥ 1.0 g/dL from Baseline and are ≥ 14 days apart, the subject will be counted as a yes in the proportion. The proportion of subjects who have an Hb increase of ≥ 1.0 g/dL from Baseline for ≥ 14 days, in the absence of RBC transfusions, in active arms will be compared to the placebo group using CMH tests. ORs, 95% CIs, and p-values will be reported. The difference in proportions (active arm-Placebo and the combined active arms-Placebo) and corresponding 95% CI will be also provided

The number and percentage of subjects who have an Hb increase of ≥ 1.0 g/dL from Baseline will be calculated at all post-Baseline Hb collection time points. For Week 24 and Week 36 data, the proportion of subjects with increases from Baseline of ≥ 1.0 g/dL in active arms will be compared to the placebo group using CMH tests. ORs, 95% CIs, and p-values will be reported. The difference in proportions (active arm-Placebo and the combined active arms-Placebo) and corresponding 95% CI will be also provided.

Proportion of Subjects who are RBC Transfusion-Free Over 36 Weeks Endpoint

The number and percentage of subjects who remain RBC transfusion free throughout the 36-week treatment period will be reported. Additionally, the number and percentage of subjects who have remained transfusion free since Baseline at each post-Baseline timepoint prior to Week 36 will be reported. Transfusion burden data will also be listed on the ITT Analysis Set.

Duration of the Mean Hb Increase from Baseline of ≥ 1.0 g/dL Over 36 Weeks

Duration of Hb increase from Baseline of ≥ 1.0 g/dL over 36 weeks will be summarized descriptively by treatment arm. The duration will be calculated according to the following:

1. Sort all post-baseline non-missing laboratory Hb values for a subject, including unscheduled, chronologically.
2. For any Hb change from baseline values that are ≥ 1.0 g/dL, compute the following:

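### SAP visit windows have no last-dose limit, so an early terminator's off-drug safety follow-up can be tabulated as a treatment week and can enter the NTDT interval-mean Hb

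*SAP*

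**What the plan says.** **Allocation rule.** SAP 10.1.10 states that "All scheduled study visits are defined relative to Study Day 1, the date of first dose", and that "A windowing convention will be used to determine the analysis visit value for a given measurement and will be applicable for all by-visit summaries". Tables 1 and 2 give the windows in study days. For vital signs, weight, ECG, hematology and chemistry the last window is Week 40, from Day 268 on. Of the visits after stopping drug, the section mentions only one: "The early discontinuation visit will be eligible for allocation to an analysis visit". When several results share a window, the one nearest the scheduled day is used, and a tie goes to the earlier. The section refers to Appendix 3 for scheduled visit windows. That appendix lists none and sets no on-treatment limit.

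**Follow-up visit.** The protocol synopsis provides for "a 4-week safety follow-up assessment after the last dose of study drug is administered". Protocol Tables 2 and 3 schedule vital signs, weight, ECG, hematology and chemistry at that visit.

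**NTDT Hb.** SAP 13.6.4.3: "Post-Baseline Hb is defined as the mean of all documented hemoglobin values collected during each 12-week interval". Values within 8 weeks after a transfusion are removed; values after last dose are not.

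**Per Protocol set.** This is the primary efficacy set. SAP 11.4 requires any post-baseline assessment and that the "subject did not discontinue prior to week 12 for reasons other than AEs". Adverse-event dropouts before Week 12 can therefore stay in.

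**Where an on-drug limit exists.** For chelation dose and serum ferritin, SAP 13.6.4.1 uses the last 12 weeks of treatment, "or the last 12 weeks of study drug for subjects who are discontinued early".

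**The concern.** The same protocol visit is handled in two ways. A completer's safety follow-up has its own Week 40 row. An early terminator's follow-up, equally four weeks off drug, goes into whichever treatment-week row its study day matches. By-visit safety tables, which are part of the primary endpoint, would then mix on-drug and off-drug values under one label.

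The NTDT Hb endpoints are more exposed because they average whatever falls in the interval. A subject who stops shortly before an interval opens can have a single value in it, taken four weeks after the last tablet. That value sets the mean change and the 1.0 g/dL responder status in the primary efficacy set.

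**Working it through.** The plan gives no figure to reproduce. The check applies its windows to its own visit schedule.

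**Inputs.** Windows from SAP Tables 1 and 2. Follow-up day = last-dose day + 28 (synopsis), with 21 and 35 as a range, assuming the ±7-day visit window. Early termination visit assumed to fall on the last-dose day. No unscheduled Hb and no transfusion.

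**Row in which the follow-up falls (+28 days)**

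| Last dose | Follow-up | NTDT | TDT vital signs | TDT ECG, labs |
|---|---|---|---|---|
| Day 56 | 84 | Week 12 | Week 12 | Week 12 |
| Day 60 | 88 | Week 12 | Week 12 | Week 12 |
| Day 84 | 112 | Week 16 | Week 15 | Week 18 |
| Day 168 | 196 | Week 28 | Week 27 | Week 30 |
| Day 224 | 252 | Week 36 | Week 36 | Week 36 |
| Day 239 | 267 | Week 36 | Week 36 | Week 36 |
| Day 240 | 268 | Week 40 | Week 40 | Week 40 |

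**How general this is.** The earliest in-window Week 36 visit is Day 252 − 7 = 245, so early last-dose days run from 2 to 244, which is 243 days.

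- At +28, Days 2 to 239 give a treatment-week row: 238/243 = 98%.
- At +21, all 243 do, since 244 + 21 = 265.
- At +35, Days 2 to 232 do (232 + 35 = 267): 231/243 = 95%.

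These are shares of possible last-dose days, not of subjects.

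**Does the early termination value displace it?** No NTDT window before Week 40 is wider than 28 days, so at +28 the two visits never share one and the follow-up is used in all 238 cases. The same holds for TDT vital signs. TDT ECG and laboratory windows reach 42 days, so the nearest-day rule sometimes picks the early termination value; the follow-up is used in 196/243 (81%).

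**NTDT Week 12-24 mean Hb.** The SAP gives no day limits for this interval, so two readings are needed.

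- *Transfusion limits of SAP 10.1.5 (Days 86-169).* The follow-up is the only value when it falls on Day 86 or later and the last dose is before Day 86: last dose Day 86 − 28 = 58 through Day 85.
- *Analysis-visit windows, Week 12 = Days 72-99.* The follow-up is the only value when it falls in that window and the early termination visit falls in Week 8 (Days 44-71): last dose Day 72 − 28 = 44 through Day 71.
- *Both readings.* Last dose Days 58-71, which includes the Day 60 example.
- *Last dose Day 84.* Counting Day 84 as inside the interval, one of two values (Days 84 and 112) is off drug. Starting at Day 86, the only value is off drug.

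**NTDT Week 24-36.** The same steps give last dose Day 170 − 28 = 142 through 169 on the first reading, Day 156 − 28 = 128 through 155 on the second, and Days 142-155 on both.

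**The case against.** Much of the case on the other side is right, and it limits the point.

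- **How many subjects have this visit.** Protocol 8.4 makes end-of-study assessments a fallback when early termination assessments are missed. Section 8.5.1 asks for appropriate follow-up before withdrawal. Only section 10.4, after unblinding, clearly requires both visits. The number affected is unknown.
- **What the SAP sentence covers.** It names the early discontinuation visit, which is reasonable to allocate. The follow-up comes in through the general study-day rule and the fixed Day 268 limit: nothing prevents it, but nothing states it as an intention.
- **Reach.** HbF, F cells, the PD-marker panel, QoL, urinalysis and coagulation are not scheduled at follow-up. Shift tables and potentially-clinically-significant counts take any post-baseline result, and TEAEs run to 30 days after last dose, so none of these depends on the windows.
- **Completers' Week 40 Hb.** The duration steps begin "Sort all post-baseline non-missing laboratory Hb values for a subject, including unscheduled, chronologically", so a reader might infer that up to 252 + 28 = 280 days could be scored for a 36-week endpoint. SAP Table 12 does not support that. It limits the 14-day endpoint to Week 36 and the duration and time-to-first-increase endpoints to 36 weeks; the rolling windows end at Day 253. What remains is a mismatch: the derivation text does not repeat those limits, and time to first increase is censored at study end date.
- **Treatment policy.** Keeping data after discontinuation can be a legitimate choice, and has some force for the ITT set. It has little for the Per Protocol set or the by-visit safety tables: section 8.5.1 withdraws subjects who stop drug, so what is kept is one isolated value rather than a continued series.

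**Conclusion.** The point stands in this limited form. Followed as written, SAP 10.1.10 puts any four-week safety follow-up of a subject whose last dose was on or before Day 239 into a treatment-week row. In NTDT such a value can be part or all of the Week 12-24 or Week 24-36 mean Hb. For last dose between Days 58 and 71 it is the whole Week 12-24 mean on either reading of the interval. This rests on a follow-up at +28 days, early termination on the last-dose day, and no unscheduled Hb or transfusion.

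A reader might infer that the rule dilutes the active arms toward placebo, chiefly through adverse-event dropouts. The documents do not establish that. They give no time course for Hb after stopping and no dropout rates by arm, and SAP 11.4 also allows subjects to be excluded for events expected to affect the analysis. The defect is a mislabelled value of unknown frequency and unknown direction of effect, worth correcting because the correction is small.

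**What to change.** 1. In SAP 10.1.10, map every End of Study (Safety FU) visit to a separate Follow-up row, whatever its study day.
2. Exclude values taken more than a stated margin after last dose from Week 1-36 analysis visits and from the Per Protocol Hb interval means, responder endpoints and rolling Hb windows. Seven days would match most protocol visit windows and keep an early termination visit that falls inside it. An ITT sensitivity analysis may retain the excluded values.
3. State the day limits of the NTDT Hb intervals, and how a subject with no remaining value is scored for response. SAP 13.6.4.2 covers transfusion and partly missing values, but not a wholly empty interval.
4. Separately, align the duration, 14-day and time-to-first-Hb text in SAP 13.6.6.3 with the 36-week limits in Table 12, so that Week 40 values cannot be counted.

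The cost is SAP wording and one derivation flag; data collection does not change. The downside is that a few early adverse-event dropouts lose their only Week 12-24 Hb value and, with no imputation planned, have no mean change for that interval.
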